4.7 General considerations

For each treatment group and biomarker, the following will be presented:

- Number and percentage of subjects screened, not randomised/assigned treatment, randomised/assigned treatment, randomised/assigned treatment and not started treatment, discontinued, and completed.
- Number and percentage of subjects randomised at each site.
- Number and percentage of subjects in each analysis set (ITT) overall and by visit.
- Number and percentage of subjects excluded from each analysis set by reason for exclusion.
- Number and percentage of withdrawals (withdraw consent to any further participation in the trial) and treatment cessation, by reason for discontinuation and visit.

5. Interim analysis and timing for analysis

No interim analysis is planned for the current trial. However, the TSC will review the accruing trial data every year during the recruitment phase of the study and assess whether there are any safety issues that should be brought to participants' attention or any reasons for the trial not to continue. TSC reports will consist of an open report where the accrual data will be described without any information on the arm patients have been allocated to, and a closed report where any safety issues by treatment arm will be presented. No stopping rule will be used. See section 9 for further detail. The trial data will be analysed following database lock.

6. Efficacy analysis

The listed measures in Table 2 are to be used in the analyses. The analyses will be carried out in STATA 18 or higher.

In hypothesis testing, the null hypothesis is rejected at (two-sided) significance level 0.05 unless otherwise specified.

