6.1 Main analyses

6.1.1 Primary endpoint

The primary endpoint of the study will be a continuous outcome of CDAI measure at 16 weeks (visit 7).

The primary analysis will assess the difference in the CDAI comparing the difference in response between the abatacept and placebo groups with the biomarker positive group against the difference in response between the abatacept and placebo groups with the biomarker negative group. This analysis will be on an ITT basis according to original randomisation allocation.

The differences between the groups on the primary outcome will be tested with a mixed-effects model with time as a continuous variable. The CDAI is measured at five time points: (1) Baseline, (2) 4 Weeks, (3) 8 Weeks, (4) 12 Weeks, (5) 16 Weeks. The baseline measurement for the primary outcome is the CDAI score after randomisation. This measurement will be included in the analysis as a covariate.

The mixed-effects model results will be presented as P values and 95% CI. In the mixed-effects model we will use both an 'unstructured' and a '1. order autoregressive' covariance matrix and choose the matrix resulting in the lowest Bayesian information criterion. To assess, if the underlying assumptions behind the mixed-effects model analysis are fulfilled, we will investigate normal quantile plots of residuals, standardized residuals, and random effects. If the underlying assumptions behind the mixed-effects model analysis are clearly violated then we will use a generalized estimation equation for the analysis.

The planned primary analysis is a mixed-effects model adjusted for centre and patient comparing the outcome of CDAI between treatment groups in the biomarker arm (Group 1) and non-biomarker arms (Group 3).

A p-value of less than 0.05 will be taken to indicate statistical significance.

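### Choosing the primary model's covariance by lowest BIC can leave a homogeneous AR(1) in place when variances differ by visit, so the week-16 standard error may be miscalibrated in either direction

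*SAP*

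**What the plan says.** Section 6.1.1 specifies a "mixed-effects model with time as a continuous variable". On visits it states: "The CDAI is measured at five time points: (1) Baseline, (2) 4 Weeks, (3) 8 Weeks, (4) 12 Weeks, (5) 16 Weeks". On the baseline value it states: "This measurement will be included in the analysis as a covariate". Read together, these leave four post-baseline outcomes per patient.

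The covariance rule is to fit the model with an unstructured and with a first-order autoregressive matrix, and then to "choose the matrix resulting in the lowest Bayesian information criterion". The section closes with: "The planned primary analysis is a mixed-effects model adjusted for centre and patient", comparing Group 1 with Group 3. Section 2.3 plans 45 patients in each of these groups.

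The opening of Section 6 sets the test: "the null hypothesis is rejected at (two-sided) significance level 0.05 unless otherwise specified". On software it says: "The analyses will be carried out in STATA 18 or higher". The SAP does not state ML or REML, whether N in the BIC counts observations or patients, a small-sample degrees-of-freedom method, or robust standard errors. It also leaves open whether AR(1) is added to a patient random effect.

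**The concern.** The covariance matrix determines the standard error, confidence interval and p-value of the primary test, and here the data choose it from only two candidates. One is fully flexible. The other has a single variance and a single correlation parameter. BIC penalises the flexible one heavily at this sample size.

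If AR(1) is kept when the residual variance differs by visit, the week-16 contrast is judged against a variance averaged over weeks 4 to 16. Where the true week-16 variance is above that average, the interval is too narrow and the false-positive rate exceeds the stated 5%. Where it is below, the test is conservative and power is lost.

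**Working it through.** **Sample size (reproduced).** For difference 10, SD 14.34, two-sided 0.05 and 90% power (Section 2.3), the normal approximation gives 44 per group. The noncentral t gives 89.9% power at 44 and 90.5% at 45, hence 45 per group. This point does not affect that figure.

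**BIC penalty.** Unstructured, four visits: 4 × 5 / 2 = 10 parameters. AR(1): 2. Difference: 8.
- N as observations: 90 × 4 = 360; 8 × ln(360) = 47.1.
- N as patients: 90; 8 × ln(90) = 36.0.

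The unstructured matrix is kept only if it raises twice the log-likelihood by more than 36 to 47.

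**Why variance can rise after adjusting for baseline.** Residual SD at a visit = SD × √(1 − r²), where r is that visit's correlation with baseline. Assume SD 13 throughout and r = 0.7, 0.6, 0.5, 0.4. The residual SDs are 9.3, 10.4, 11.3 and 11.9. Even if the raw five-visit series is exactly AR(1) with ρ = 0.7, the residual variance fractions 1 − ρ^(2k), for k = 1 to 4, are 0.51, 0.76, 0.88 and 0.94. A homogeneous AR(1) then no longer fits the residuals.

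**Simulation A: residual covariance set directly.** 45 per group, 4,000 null trials per scenario, complete data, ML, Wald z at 1.96, linear time by group, week-16 contrast. There were 13 assumed covariances, 12 of them not AR(1). Type I error after selection uses BIC on observations.

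| Assumed residual covariance | AR(1) kept, N = 360 / N = 90 | Type I error, BIC rule |
|---|---|---|
| Constant variance, random intercept + AR(1) | 99.8–100% / 97–99.9% | within 4.9–6.4% |
| Constant variance, compound symmetry 0.5 | 87% / 57% | within 4.9–6.4% |
| Constant variance, compound symmetry 0.7 | 44% / 13% | within 4.9–6.4% |
| AR(1) correlation, SD rising 10 to 14 | 99% / 93% | 9.5% |
| AR(1) correlation, SD rising 8 to 14 | 55% / 21% | within 5.9–9.5% |
| Compound symmetry 0.6, SD rising 8 to 14 | 2% / 0.1% | within 5.9–9.5% |
| Random intercept + slope | 63% / 26% | 8.7% |
| AR(1) correlation, SD falling 14 to 10 | 99% / 93% | within 2.1–3.7% |

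- Fixing the unstructured matrix in advance gave 5.2–6.7% in all 13 scenarios. The small excess over 5% comes from ML with a z reference.
- With SD rising 10 to 14, the AR(1) model SE averaged 2.49 against an empirical 2.90, a ratio of 0.86.
- With SD falling 14 to 10 (categorical-time version), they were 2.51 and 2.09, a ratio of 1.20.
- Monte Carlo error at 9% is √(0.09 × 0.91 / 4000) = 0.45 percentage points.
- Adding a patient random intercept to AR(1) gave 5.1–5.8% with constant variance, but still up to 9.4% with rising variance.

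**Simulation B: raw five-visit covariance set, baseline then conditioned on.** Same design, correlation falling linearly from 0.7 (adjacent visits) to 0.4 (baseline to week 16). Ranges are over repeated runs.
- SD 14 falling to 12: 7.3–7.9%.
- SD constant at 13: 8.0–8.6%.
- SD 11 rising to 14: 9.6–10.4%.
- Raw series exactly AR(1), ρ = 0.7 and 0.8, 2,000 trials each: AR(1) kept in 99.8% and 97%; type I error 9.2% and 10.2%, against 6.7% for unstructured.

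In the first three scenarios AR(1) was kept in 92–100% of trials with BIC on observations. Unstructured with REML and a t reference gave 5.6–5.9%.

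**The case against.** The rule is written down in advance, and BIC does detect strong departures. The excess error depends on a correlation pattern the SAP does not contain. In the first three Simulation B scenarios the variance conditional on baseline rises, even where the raw SD falls from 14 to 12 (residual variances 93, 108, 117, 121). That scenario matches the SAP's SD of change exactly: √(14² + 12² − 2 × 0.4 × 14 × 12) = 14.34. It also shows the smallest excess, 0.9 to 1.7 percentage points over unstructured.

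Section 6.1.1 also describes a contrast using all four groups. At 90 per group AR(1) is kept less often: 27% under compound symmetry 0.5, and 53% when the raw SD rises 11 to 14. The section adds residual checks and a GEE alternative.

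Much of this stands. The direction cannot be proved, and the harm comes from the equal-variance assumption; BIC only lets it through. But the larger sample is not a cure: with residual SD rising 10 to 14 at 90 per group, AR(1) was kept in 91% of trials (BIC on observations) and the type I error was 8.2%. The GEE switch does not close the gap either. Its trigger is normal quantile plots, which do not target unequal variances by visit, and no robust standard errors are stated.

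**Conclusion.** The rule can leave the week-16 standard error miscalibrated, in a direction the SAP does not allow one to predict. Under assumed covariances the type I error is roughly 8–10% when variance conditional on baseline rises over visits, somewhat less where the rise is mild or steep enough for BIC to detect. It is about nominal when that variance is flat and about 2–4% when it falls. The comparator is about 5–7% for a fixed unstructured matrix with ML and z.

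A reader might infer that BIC will pick AR(1) almost every time, and that this necessarily understates the standard error and inflates the type I error. The documents do not support that. AR(1) was kept in anything from 2% to 100% of trials, and in over 90% in only 5 of 12 non-AR(1) scenarios (BIC on observations). A wrong correlation with constant variance did no harm at week 16.

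The one SD given, 14.34 for change, does not settle the direction. With correlation 0.4 to baseline, SD 13 throughout gives an SD of change of 14.24 and a type I error of about 8%. SD 15 falling to 9.5 gives 14.19 and 5.8%, against 6.6% for unstructured.

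All covariance scenarios are assumptions, as are complete data and a week-16 contrast. The point justifies a cheap improvement to the plan. It does not show that the primary test is invalid.

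**What to change.** In Section 6.1.1:
- Delete the BIC selection.
- Pre-specify an unstructured residual covariance for the four post-baseline visits, fitted by REML with Kenward-Roger or Satterthwaite degrees of freedom.
- Drop the separate patient random intercept, since the unstructured matrix already carries within-patient dependence.
- Name a fallback for non-convergence: a heterogeneous-variance structure such as heterogeneous Toeplitz, or robust standard errors.
- Report AR(1) only as a sensitivity analysis.

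This changes SAP wording only and leaves the sample size untouched. The downside is a slightly wider interval in some cases and a small chance of needing the fallback.

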6.1.2 Secondary analyses

The following secondary endpoints will be reported descriptively within each treatment group:

- 1) Percentage of patients with DAS28(ESR)<3.2 (LDA) at 16 weeks
- 2) Percentage of patients with CDAI ≤10 (LDA) at 16 weeks

- 3) Percentage of patients with CDAI remission at 16 weeks
- 4) Change in HAQ-DI at 16 weeks from baseline
- 5) Change in SF-36 at 16 weeks from baseline

Comparisons by groups will be guided by those performed for the primary endpoint in accordance with the following testing outlined above for the primary analysis:

1 vs 3

1 + 2 vs 3+4

All comparisons involving continuous secondary outcomes will be carried using mixed-effects models comparing treatment groups at 16 weeks, adjusted for baseline score, patient and centre. The associated absolute change difference and 95% confidence interval, as well as the mean change in each group will be reported.

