2.1 Study objectives

Primary objective: The primary objective of this trial is to determine whether synovial molecular profiles (=drug target signatures) can inform treatment response to abatacept in early RA..

To this aim, we will compare the change in Clinical Disease Activity Index (CDAI) score at 16 weeks between the biomarker positive and the biomarker negative patients within the abatacept group (i.e. Group 1 vs Group 3) Fig.1 Study Scheme diagram. The primary trial hypothesis is that biomarker positive patients treated according to their highest expressed biomarker will have lower CDAI response at 16 weeks compared to biomarker negative patients.

[figure not shown]
This primary analysis has been chosen as we want to establish a difference in response rates in the treatment in the biomarker arm first, and the trial has been powered for this.

Secondary objectives:

The following analysis will be done:

- Compare patients treated according to their biomarker in the intervention arm against the control arm as a whole (i.e. Group 1 vs 3+4), to determine the enrichment in response in the treatment allocation arm vs the standard of care response rate.
- II. Assess the efficacy of treatment allocation according to biomarker compared to random allocation, we will compare the biomarker positive patients in the intervention arm vs the biomarker positive patients in the control arm (i.e. Group 1 vs Group 4)
- III. Assess the efficacy of the strategy as a whole against the current clinical practice by comparing the control vs intervention arm (i.e. Groups 1 + 2 vs Group 3+4)

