3.3.2 Secondary endpoints

- 1) Percentage of patients with DAS28<3.2 (LDA) at 16 weeks.
- 2) Percentage of patients deemed responders using American College of Rheumatology 50 (ACR50) measure at 16 weeks.
- 3) Percentage of patients with CDAI remission at 16 weeks.
- 4) Change in HAQ-DI at 16 weeks from baseline.
- 5) Change in SF-36 at 16 weeks from baseline

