6.7 Statistical analysis issues

6.7.1 Multiple comparisons

The primary and secondary analyses will be carried at 5% significance level. Since one primary endpoint will be analysed, no correction for multiplicity will be applied. Many of the secondary outcome measures are expected to be highly correlated with the primary outcome measure, their analyses will be considered as confirmatory of the primary endpoint. Sub- group analyses are regarded as descriptive and will not be accompanied by formal hypothesis testing.

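### The SAP's lists of secondary endpoints and comparisons contradict each other, and section 6.7.1 gives uncorrected secondary tests confirmatory weight because they correlate with the primary

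*SAP*

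**What the plan says.** **Endpoints.** Section 3.3.2 lists five secondary endpoints. The first is "Percentage of patients with DAS28<3.2 (LDA) at 16 weeks" and the second is "Percentage of patients deemed responders using American College of Rheumatology 50 (ACR50) measure at 16 weeks". The other three are CDAI remission, change in HAQ-DI and change in SF-36. Section 6.1.2 also lists five. Its first is "Percentage of patients with DAS28(ESR)<3.2 (LDA) at 16 weeks" and its second is "Percentage of patients with CDAI ≤10 (LDA) at 16 weeks", followed by the same last three.

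**Comparisons.** Section 2.1 says that three secondary analyses will be done. Objective I compares patients treated by biomarker "against the control arm as a whole (i.e. Group 1 vs 3+4"). Objective II compares the biomarker-positive patients of the intervention arm "vs the biomarker positive patients in the control arm (i.e. Group 1 vs Group 4"). Objective III compares Groups 1+2 with Groups 3+4. Section 6.1.2 lists 1 vs 3 and 1+2 vs 3+4, and presents both as following the testing set out for the primary analysis. It gives a model (mixed-effects, adjusted for baseline score, patient and centre) for continuous secondary outcomes only.

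**Inferential status.** Section 6.7.1 sets a 5% level for primary and secondary analyses and applies no multiplicity correction because there is one primary endpoint. It notes that many secondary outcomes should correlate highly with the primary, and concludes that "their analyses will be considered as confirmatory of the primary endpoint".

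**The concern.** A SAP should let a statistician who has not seen the data work out which outcomes to analyse, between which groups, by which model, and what each result may support. On the secondary analyses this one gives two different answers to the first two questions, a partial answer to the third, and a doubtful answer to the fourth.

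Whoever runs the analysis must choose between ACR50 and CDAI ≤10 as the secondary response measure, and decide on which outcome and by which model to test 1 vs 3+4 and 1 vs 4. Objective II matters most here, because section 2.1 makes it the test of allocation by biomarker against random allocation. If these choices are left until after database lock, they can be made with results in view.

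The rule in section 6.7.1 raises the stakes. Having a single primary endpoint is a reason not to adjust the primary test. It is no reason to give unadjusted tests on other outcomes confirmatory weight. The correlation argument also works against the rule: outcomes that move with the primary in the same patients share its chance imbalances, so if the primary is a false positive, they will tend to be false positives too.

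**Working it through.** **1. Endpoint lists side by side**

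| Section 3.3.2 | Section 6.1.2 | Match |
|---|---|---|
| DAS28 <3.2, version not named | DAS28(ESR) <3.2 | Partial |
| ACR50 | not listed | Only in 3.3.2 |
| not listed | CDAI ≤10 | Only in 6.1.2 |
| CDAI remission | CDAI remission | Yes |
| HAQ-DI change | HAQ-DI change | Yes |
| SF-36 change | SF-36 change | Yes |

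Four of five are shared, one of them with its version stated in only one place. ACR50 has not been moved to the exploratory list: section 3.3.3 names ACR20/70 only. Section 6.4 lists ACR50 as a generated variable, but that only derives it.

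**2. Comparison lists side by side**

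| Comparison | Section 2.1 | Section 6.1.2 |
|---|---|---|
| 1 vs 3 | Primary | Listed |
| 1 vs 3+4 | Objective I | Not listed |
| 1 vs 4 | Objective II | Not listed |
| 1+2 vs 3+4 | Objective III | Listed |

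One of three secondary objectives is carried into section 6.1.2. That section attributes its list to the primary analysis, but section 6.1.1 contains no 1+2 vs 3+4 test.

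**3. Scale of the uncorrected testing**

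The SAP gives no error rate, power or sample size for the secondary comparisons, so there is no stated figure to reproduce for them. Its one related figure is the primary sample size in section 2.3: difference 10, SD 14.34, 90% power, here with the two-sided 5% of section 6. The normal formula gives 2 × (1.960 + 1.282)² × 14.34² / 10² = 43.2, so 44 per group. The t-test version gives 44.2, so 45 per group, or 90 in all, as stated. The present point does not touch it.

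Inputs for the secondary tests:
- two-sided level 0.05 per test (sections 6 and 6.7.1);
- 5 endpoints × 2 comparisons in section 6.1.2 = 10 tests;
- of these, 2 continuous endpoints × 2 comparisons = 4 tests with a stated model;
- correlation between test statistics: **assumed**, since the SAP gives none.

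If the tests are independent and all nulls are true, the chance of at least one false positive is 1 − 0.95^k:
- k = 10: 1 − 0.95^10 = 0.401
- k = 4: 1 − 0.95^4 = 0.185

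If the k statistics are standard normal with a common correlation ρ, it is 1 − P(all |Z| < 1.96), found by integrating over the shared component:

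| Tests | ρ = 0 | 0.5 | 0.7 | 0.8 | 0.9 |
|---|---|---|---|---|---|
| 10 | 40.1% | 28.7% | 21.3% | 17.3% | 12.8% |
| 4 | 18.5% | 15.6% | 13.0% | 11.4% | 9.4% |

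Correlation lowers the rate, but in none of these cases does it bring it down to 5%.

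**The case against.** Three stronger readings are tempting, and the SAP does not support them.

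- *The same tests are called both descriptive and confirmatory.* Section 6.1.2 does say "The following secondary endpoints will be reported descriptively within each treatment group", but that concerns summaries within each group. The between-group comparisons follow in a separate paragraph. Summarising groups and then comparing them is ordinary practice. In section 6.7.1, the analyses called descriptive are the subgroup analyses.
- *Objectives I and II are never analysed.* Section 2.1 names both contrasts and says they will be done. They could be read as further contrasts on CDAI, with section 6.1.2 covering only the secondary endpoints. What can be shown is narrower: section 6 gives them no endpoint and no model.
- *ACR50 goes unanalysed.* Section 6.4 keeps it as a generated variable. Table 2 includes a logistic regression whose outcome labels are not fully readable in the text at hand. The proven fault is inconsistent status, not absence of any analysis.

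Two milder objections carry some weight. *Confirmatory* may have been meant as *corroborating*, and unadjusted secondary tests beside a single primary are common. If that was the intention, changing the word costs nothing. As written, though, the sentence lets significant secondary results be cited as confirmation. Also, section 1 requires written agreement to changes during the trial, and deviations must be justified in the final report. A late choice would therefore not be invisible. But choosing between two lists that both stand in the SAP need not count as a change or a deviation, so the ambiguity remains.

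The error rates are soft. Independence is unrealistic, given that section 6.7.1 itself expects high correlation with the primary and the two comparisons share Groups 1 and 3. The lower end of the table is the more plausible part.

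**Conclusion.** The point holds as a contradiction between lists and a faulty inferential rule. One secondary endpoint differs outright between sections 3.3.2 and 6.1.2 (ACR50 against CDAI ≤10), and a second differs in whether its DAS28 version is named. Two of the three secondary comparisons promised in section 2.1 have no endpoint or model in section 6. Section 6.7.1 grants confirmatory weight to uncorrected tests, and neither of its reasons supports this.

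The lists can be checked by reading and rest on no assumption. The error rates are for scale only. They rest on the test counts (10, or 4 with a stated model), all nulls being true, and correlations that the SAP does not supply. The primary analysis and its sample size are unaffected. This should be corrected, but it does not threaten the primary result.

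**What to change.** Before unblinding:

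1. Use one list of secondary endpoints in sections 3.3.2 and 6.1.2. Settle ACR50 versus CDAI ≤10, list the other as exploratory, and state the DAS28 version in both places.
2. Carry 1 vs 3+4 and 1 vs 4 into section 6 with a named endpoint (CDAI change at least) and a model. Correct the statement that the 6.1.2 comparisons follow the primary analysis, since 1+2 vs 3+4 does not appear there.
3. State a model for the binary secondary endpoints.
4. In section 6.7.1, replace *confirmatory* with *supportive* and report estimates with 95% confidence intervals. If the sponsor wants formal secondary claims, prespecify a fixed sequence that is tested only after a significant primary result.

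The cost is SAP wording, with no effect on sample size or conduct. The downside is that, without a prespecified sequence, secondary p-values can no longer be cited as confirmation of the primary result.
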